## Research Overview

The purpose of this research is to assess various methods of framing NHTSA's CPS recommendations, as well as the scope of the information provided. This project will conduct two experimental studies. Data will be collected from parent participants in two large metropolitan statistical areas on the east coast of the United States. In the first study, participants (N= 300) will be randomized into one of five groups to examine relative effectiveness of, and parent preferences for, different methods of framing CPS recommendations. That is, the goal of the first study is to determine HOW to best communicate the recommendations to parents (e.g., should we include information regarding risk- reduction/rationale, should we emphasize the "hardest sell" for advocates over all other information, etc.). In the second study, participants (N= 240) will be randomized into one of four groups to examine the relative effectiveness of CPS recommendations delivered in combination with other types of information. That is, the goal of the second study is to determine the type and amount of EXTRA information to include in the recommendations without losing the clarity and power of the key recommendations (e.g., normative information is often included but theoretically is contra-indicated, installation information is not included but theoretically may be necessary, etc.). It is hoped that the findings of this research inform the development of more effective ways to communicate messages for child passenger safety. These studies and their methods are explained in detail in the sections that follow.

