### *Sampling Plan*

The geographic regions in which the study will take place include two large Metropolitan

Statistical Areas (MSAs): Philadelphia – Camden – Wilmington (Delaware Valley) and Virginia Beach – Norfolk – Newport News (Hampton Roads). The Delaware Valley MSA includes 13 counties in four States with a population of over 5.9 million people. The Hampton Roads MSA includes 10 cities and six counties in two States (VA-NC), with a population of over 1.6 million. These are two socio-economical and culturally diverse areas that range from the rural areas of VA's Eastern Shore and PA's farming communities, to large concentrations of people living in urban and suburban settings.

The sample will include 300 parents of children ages 0-12 years. Although expected to be a convenience sample, efforts will be made during recruitment and screening of participants to ensure that the sample under study is representative of the larger population, and that the study includes a variety of income levels, education levels, and racial/ethnic groups (at least Black, White, Latino) across the study conditions.

Power analysis indicated that a sample of 196 participants is adequate to detect small effect sizes above Cohen's  $d = 0.25$  with a statistical power of 0.80 at the standard significance level of  $\alpha = .05$ . Equal variance between groups is expected due to random assignment. Effect sizes for similar studies of intervention messages with smaller sample sizes and fewer experimental groups have been in the medium to large range (Cohen's  $d = .50$  to 1.68) (Will, Sabo, & Porter, 2009). Therefore, the sample size of 300 participants will be ample to detect group differences in this study.

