## **Measures**

Several measurement scales will be used to assess appropriateness of restraint selection, knowledge of restraints, perceived efficacy and threat, attitudes and intentions, judgments of relevance and acceptability of the CPS information, and sample demographics. To accurately assess changes in knowledge and perceptions after exposure to the independent variable, most measures will be asked both at pretest and posttest. The exceptions are the demographics questions and judgments of relevance and acceptability, which will be asked only at posttest (see survey attachment in Appendix H).

*Restraint Selection Task.* A key dependent variable for Study 1 is proper child restraint selection; thus, a Restraint Selection Task was developed that provides participants with a series of specific scenarios that ask the participants to select an appropriate restraint, direction to face, and/or vehicle row, given specific age/weight/height information for a hypothetical child. This 8-item knowledge measure uses a multiple choice response format (providing an item score of correct/incorrect and a total number correct score for each participant). This measure was adapted

from a similar existing field-tested measure (Snowden et al., 2008).

*Knowledge of Restraint.* To gauge immediate changes in knowledge of child passenger safety, as well as differences in knowledge among the groups, a 15-item assessment of parental knowledge will be conducted at both pretest and posttest. This measure uses a Likert-type response format and was tailored for this study from existing field-tested and validated measures used in past research by Snowden and colleagues (2008, 2009), and Will and colleagues (2009). Many questions originated from the Co-Investigators Kids in Kars Survey which has excellent internal consistency ( $\alpha = .92$ ) and measures parents' knowledge of and attitudes toward recommended guidelines for restraint use (Will, Sabo, & Porter, 2009).

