### ***Data Analysis Plan***

Data analysis will determine which CPS recommendation version produces the maximum desired outcome (e.g., correct CPS restraint selection, increased knowledge of restraints, enhanced perceptions of efficacy and risk). Data analysis will begin with data cleaning such as checking for missing data and outliers and ensuring normality and linearity of all dependent variables. Next, bivariate correlations will be conducted on all dependent variables to assess their relation to each other and to determine the type of inferential statistics to conduct. Specifically, if dependent variables are moderately inter-correlated, then a 2 (Time) x 5 (CPS Recommendation Version) MANOVA with follow-ups, post-hoc test for group, and simple effects analyses (if the interaction is significant) will be conducted. If dependent variables exhibit inter-correlations near zero or are highly inter-correlated, then multiple 2 (Time) x 5 (CPS Recommendation Version) ANOVAs with post-hoc test for group and simple effects analyses (if the interaction is significant) will be conducted. In the event that the data are found to violate the assumptions of normality that are necessary for parametric tests, data transformations to improve normality or appropriate nonparametric tests, such as the Friedman test and follow-up Multiple Comparison Tests, will be performed instead. Additionally, the study team may conduct several secondary analyses, including a multiple regression for CPS restraint selection to determine which CPS recommendation version best predicts correct restraint selection. Also, variables such as perceived relevance and accuracy of CPS information, age, sex, race, education, income, number of children, and ages of children may be used as covariates to eliminate potential confounding variables and better explain variance in the analyses. The results of Study 1 will be written into a brief research report for NHTSA. No reports or presentations will identify individual participants.

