### ***Sampling Plan***

Participants for Study 2 will be drawn from the same two broad geographic regions (Delaware Valley MSA and Hampton Roads MSA) as Study 1, with the same procedures followed for assurance of representativeness of the convenience sample. The sample will include 240 parents of children ages 0-12 years. An added exclusion criterion for Study 2 will be that the participants cannot have participated in Study 1.

Power analysis indicated that a sample of 179 participants is adequate to detect small effect sizes above Cohen's  $d = 0.25$  with a statistical power of 0.80 at the standard significance level of  $\alpha = .05$ . Equal variance between groups is expected due to random assignment. Effect sizes for similar studies of intervention messages with smaller sample sizes and fewer experimental groups have been in the medium to large range (Cohen's  $d = .50$  to 1.68) (Will, Sabo, & Porter, 2009). Therefore, the sample size of 240 participants will be ample to detect group differences in this study.

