## **Data Analysis Plan**

Analyses will determine which CPS information combination produces the maximum desired outcome (e.g., correct CPS restraint selection, increased knowledge of restraints, increased perceptions of efficacy and risk, increased knowledge of common mistakes). This will initially consist of data cleaning such as checking for missing data and outliers and ensuring normality and linearity of all dependent variables. Next, bivariate correlations will be conducted on all dependent variables to assess their relation to each other and to determine the type of inferential statistics to conduct. Specifically, if dependent variables are moderately correlated, then a 2 (Time) x 4 (CPS Information Combination) MANOVA with follow-ups, post-hoc test for group, and simple effects analyses if the interaction is significant will be conducted. If dependent variables exhibit correlations near zero or are highly correlated, then multiple 2 (Time) x 4 (CPS Information Combination) ANOVAs with post-hoc test for group and simple effects analyses if the interaction is significant will be conducted. In the event that the data are found to violate the assumptions of normality that are necessary for parametric tests, data transformations to improve normality or appropriate nonparametric tests, such as the Friedman test and follow-up Multiple Comparison Tests, will be performed instead. Additionally, the study team may conduct several secondary analyses, including a multiple regression for CPS restraint selection to determine which CPS information combination best predicts correct restraint selection. Also, variables such as perceived relevance and accuracy of CPS information, age, sex, race, education, income, number of children, and ages of children may be used as covariates to eliminate potential confounding variables and better explain variance in the analyses.

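### Observed correlations, with no cut-offs, choose between one MANOVA and separate ANOVAs over six or seven outcomes; no outcome is decisive and no error control across outcomes is stated

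*Protocol*

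**What the plan says.** The Study 1 Data Analysis Plan states that "bivariate correlations will be conducted on all dependent variables to assess their relation to each other and to determine the type of inferential statistics" to be used. Moderate correlations lead to a Time by Version MANOVA with follow-ups. For the other two situations the text reads "If dependent variables exhibit inter-correlations near zero or are highly inter-correlated, then multiple 2 (Time) x 5 (CPS Recommendation Version) ANOVAs". The Study 2 Data Analysis Plan repeats the rule: "If dependent variables exhibit correlations near zero or are highly correlated, then multiple 2 (Time) x 4 (CPS Information Combination) ANOVAs". Neither section defines moderate, near zero or high.

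Both sections aim to find the version or combination that performs best, and both give the outcomes only as examples. Under Measures, Study 1, the protocol says "A key dependent variable for Study 1 is proper child restraint selection", which is one key variable and not a declared primary. The significance level appears only in the two Sampling Plan sections, "with a statistical power of 0.80 at the standard significance level of" .05. The post-hoc and multiple-comparison tests that are mentioned are not named, and they compare groups, not outcomes.

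**The concern.** A confirmatory analysis should be fixed before the outcome data are seen. Here two analysts could follow the text faithfully and run different tests on the same data, because the boundary words have no numbers. The rule also treats the outcomes as one block. Six outcomes give 15 pairwise correlations and seven give 21, and a mixture of weak, moderate and strong pairs is a realistic result for which the plan has no instruction.

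The rule sends outcomes with near-zero correlations to separate tests, which is where testing many outcomes inflates error most. Because no outcome is decisive, a version could be declared best on whichever scale happens to favour it. The Research Overview says the findings are meant to inform how child passenger safety messages are communicated, so a chance winner could carry through into public advice.

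**Working it through.** **The plan's own figures.** Study 1 states "Power analysis indicated that a sample of 196 participants is adequate to detect small effect sizes above Cohen's" d = 0.25, and Study 2 states "Power analysis indicated that a sample of 179 participants is adequate to detect small effect sizes above Cohen's" d = 0.25. A one-way ANOVA F test at .05 with effect f = 0.25 and noncentrality N × f² reproduces both numbers:
- N = 196 with five groups gives power 0.8005.
- N = 179 with four groups gives power 0.8015.

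The match is to Cohen's f, although the text says d. That is a separate matter. What counts here is that each study was sized for one test at .05, with no division over outcomes. The protocol states no family-wise error rate to reproduce.

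**Number of outcomes.** The Study 1 Measures give these pre-post outcomes: restraint selection, knowledge, RBDS efficacy, RBDS threat, attitudes and intentions. That is six, if the RBDS is scored as its two subscales. Study 2 adds the installation subscale, making seven. The relevance and acceptability judgments are collected only at posttest, so they cannot enter a Time by group model and are not counted. Pairs: 6 × 5 / 2 = 15 and 7 × 6 / 2 = 21.

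**ANOVA branch, independent outcomes.** With one group-by-time test per outcome at .05 and no true effects:
- Six outcomes: 1 − 0.95⁶ = 0.265.
- Seven outcomes: 1 − 0.95⁷ = 0.302.

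**ANOVA branch, correlated outcomes.** The simulation used equicorrelated change scores, one F test per outcome, no true effects and 40,000 runs per setting. Group size was 60 (300/5 and 240/4, assuming equal allocation).

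| Correlation | Study 1: 5 groups, 6 outcomes | Study 2: 4 groups, 7 outcomes | Branch under the rule |
|---|---|---|---|
| 0 | 26.1% | 30.3% | ANOVAs |
| 0.5 | 21.7% | 24.0% | MANOVA, so not applicable |
| 0.7 | 17.5% | 18.6% | ANOVAs, if this counts as high |
| 0.8 | 14.7% | 15.6% | ANOVAs |
| 0.9 | 11.1% | 12.0% | ANOVAs |

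The assignment of correlation values to branches is an assumption, since the protocol gives none.

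**MANOVA branch.** If nothing differs and follow-ups run only after a significant omnibus test, the chance of a false finding is at most 5%. That protection ends once one outcome truly differs, because the omnibus test then opens the way to the follow-ups on every other outcome. This was simulated for Study 1 with five groups of 60 and six outcomes. One outcome was shifted in the control group only, and follow-ups were run at .05 after a significant MANOVA. The chance of a false positive among the other five outcomes was:
- shift 0.5 SD, correlation 0.3 to 0.5: about 17–18%;
- shift 0.8 SD, correlation 0.3 to 0.5: about 19–21%.

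Allowing for variation between runs, the range is about 17–22%. The ceiling for five independent outcomes with no protection is 1 − 0.95⁵ = 0.226. The shifts are assumptions. They lie within the d = .50 to 1.68 that the Sampling Plan cites for similar messages, and the Study 1 control group receives no safety instruction between the two tests.

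**With adjustment.** Bonferroni over independent outcomes (.05/6 = .0083 or .05/7 = .0071) brings the chance back to 4.9%.

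**The case against.** A reader might infer that the whole plan carries a false-positive risk of about 21–30%. The documents do not support that. The lower end of such a range comes from running separate ANOVAs at a correlation of about 0.5, where the rule calls for the MANOVA. The risk has to be stated branch by branch, and the high-correlation branch lies well below 21%.

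A reader might also infer that the tests are declared unadjusted. They are not. The protocol neither states nor excludes adjustment across outcomes, and an analysis plan that is not shown could supply it. This part of the objection stands, so every figure here is conditional on testing each outcome at .05. The selection rule and the open list of outcomes, however, are written in the protocol itself.

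Nor do the documents show that group comparisons add further to these figures. Simple effects follow only a significant interaction, so with no true effects they cannot raise the chance of a first false omnibus result.

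Three more points are fair:
- The outcomes concern one subject in the same parents, and the knowledge and attitude scales draw partly on one survey, so correlations near zero throughout are the least likely case.
- The rule looks at correlations among outcomes, not at which version wins. No inflation from the choice itself has been calculated; the figures are multiplicity within each branch.
- Restraint selection is called key for Study 1 only. Two of the four Study 2 conditions carry installation tips, and an installation subscale was added for that study, so the same primary outcome cannot simply be assumed there.

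**Conclusion.** The concern holds in this form. The protocol fixes a rule that lets observed correlations choose the main analysis, without cut-offs and without an answer for a mixed pattern. It also leaves the best-version conclusion without a decisive outcome or any stated control across outcomes.

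If each outcome is tested at .05, the chance of at least one false group-by-time effect is about 26–30% in the near-zero branch and about 11–19% in the high-correlation branch. The MANOVA branch is safe only when nothing differs at all. With one real difference in Study 1, the remaining outcomes carry about 17–22%.

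These sizes rest on the RBDS being scored as two subscales, one test per outcome, equal allocation, equal correlations among outcomes, and the assumed correlations and shifts. The gap in the rule itself depends on none of them. This should be changed before the data are analysed.

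**What to change.** - Drop the correlation-based choice and prespecify one analysis for each study.
- Study 1: name the Restraint Selection Task total-correct score as the primary outcome, tested at .05, and base the best-version conclusion on it.
- Study 2: have the sponsor name the primary outcome in advance, either restraint selection or installation knowledge, or test both with Holm adjustment.
- Both studies: list the remaining outcomes in full, in place of examples, and test them as secondary with Holm adjustment.

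The cost is a change of analysis wording, with no change to sample size, measures or procedures. The downside is that secondary outcomes face a stricter threshold, as would the two Study 2 candidates if both are kept. For Study 2 the sponsor must also decide which outcome matters most, which the protocol has so far left open.

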## Study 1 Methods

### *Study Design*

For Study 1, a 5 (CPS Recommendation Version) X 2 (Time) experiment will use a randomized controlled trial design to examine relative effectiveness of and parent preferences for different methods of framing child passenger safety recommendations. As described in more detail below, parent participants will be electronically randomized to one of five groups (including four experimental conditions and one control group), and will respond to pre-post surveys.

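### The only nonparametric test named as a fallback, the Friedman test, does not compare the randomised groups in either study

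*Protocol*

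**What the plan says.** Study 1 is described under Study Design: "a 5 (CPS Recommendation Version) X 2 (Time) experiment will use a randomized controlled trial design", and "parent participants will be electronically randomized to one of five groups". Study 2 has the same structure with four groups. Under Measures, "most measures will be asked both at pretest and posttest".

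The Study 1 Data Analysis Plan states the question as one between groups: "Data analysis will determine which CPS recommendation version produces the maximum desired outcome". The planned analysis is a Time x Group MANOVA or a set of "ANOVAs with post-hoc test for group and simple effects analyses (if the interaction is significant) will be conducted".

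The fallback clause opens "In the event that the data are found to violate the assumptions of normality that are necessary for parametric tests". It then offers "data transformations to improve normality or appropriate nonparametric tests", and the one nonparametric test it names is Friedman: "appropriate nonparametric tests, such as the Friedman test and follow-up Multiple Comparison Tests, will be performed instead". The Study 2 Data Analysis Plan repeats the clause. Neither plan names a nonparametric test for independent groups or for the Time x Group interaction.

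**The concern.** The Friedman test has one factor, and that factor must vary within a block. Here the block is the parent, and the only thing that varies within a parent is time. The five (or four) groups contain different, unmatched parents, so group cannot be the Friedman factor.

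The test therefore replaces a model for group and group-by-time with a test of time alone. Parents are likely to score better on items they have just read about, whichever version they saw. A significant Friedman result would be easy to obtain and could be misread as evidence about the messages. A real difference between versions would have no test at all.

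The fallback could plausibly be reached. The key outcome in Study 1 is a number-correct score on 8 items, and several other outcomes are bounded Likert-type scales. The plans check normality of the dependent variables but set no test or threshold.

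**Working it through.** **1. What the trial was sized for.** The Sampling Plans give 196 (Study 1) and 179 (Study 2) for an effect of 0.25, power 0.80 and alpha .05. I took a one-way between-group F test with noncentrality λ = N·f² and f = 0.25.

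- Study 1, k = 5: λ = 196 × 0.0625 = 12.25 on 4 and 191 df. Power is 0.801, and the smallest N reaching 0.80 is 196.
- Study 2, k = 4: λ = 179 × 0.0625 = 11.19 on 3 and 175 df. Power is 0.802, and the smallest N is 179.

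Both figures reproduce exactly, so the sample sizes rest on a between-group comparison. (They reproduce with 0.25 read as Cohen's f, whereas the text labels it d. That is a separate matter.)

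**2. What Friedman becomes with two time points.** With n blocks and k = 2 conditions,

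Q = 12/[n·k·(k+1)] × ΣR² − 3n(k+1) = (2/n)(R_pre² + R_post²) − 9n.

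Let p parents improve and m worsen, with n = p + m. The rank sums are R_post = 2p + m and R_pre = p + 2m, so ΣR² = 5p² + 8pm + 5m². Then

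Q = [2(5p² + 8pm + 5m²) − 9(p + m)²]/(p + m) = (p − m)²/(p + m), on 1 df.

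This is the sign test. The tie-corrected form gives the same expression once parents with no change are dropped. Only the totals p and m enter, and group does not appear. As a check, parents in one simulated data set were permuted across groups, and the p-value was 9.4 × 10⁻¹⁰ before and after. With two time points there is one pair, so follow-up multiple comparisons are empty.

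**3. Expected result when every version works equally well.** Assumptions: 300 parents, SD 1, pre-post correlation 0.5, and a gain of 0.5 SD in all five groups. The change score has SD √[2(1 − 0.5)] = 1, so the chance of improving is Φ(0.5) = 0.691. Expected p = 207.4 and m = 92.6, giving Q ≈ (114.9)²/300 = 44.0 against a critical value of 3.84. Rejection is practically certain although the versions do not differ.

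**4. Simulation.** I assumed 60 parents per group; the protocol does not state the allocation ratio. The effect sizes are also assumptions. The comparator is Kruskal-Wallis on pre-post change for the continuous scores (4,000 runs) and rank ANCOVA across arms for the 8-item binomial scores (2,000 runs).

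| Scenario | Friedman rejects | Between-group rank test rejects |
|---|---|---|
| Continuous, 5 groups, equal gain 0.5 SD | 100% | 5.1% |
| Continuous, 5 groups, gains −0.5, −0.25, 0, 0.25, 0.5 SD | 4.4% | 99.9% |
| Continuous, 5 groups, gain 0.5 SD in four, 0 in control | 100% | 76.3% |
| Continuous, 4 groups, equal gain 0.5 SD | 100% | 5.0% |
| 8 items, 5 groups, all from 50% to 60% correct | over 99.9% | 4% to 5% |
| 8 items, 5 groups, two gain 15 points, two lose 15, one unchanged | 3% | 100% |

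In the third row both tests reject often, but Friedman's rejection reflects the overall gain. It gives the same answer as in the first row, where there is no version effect.

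**The case against.** A reader might infer that, if normality fails, the analysis will test only change over time. The protocol does not support that. The same sentence offers transformation first, and that keeps the Time x Group model. Friedman is introduced as an example of an appropriate test, so an analyst could choose a between-group rank test and still comply. The main analysis is sound on this point, and both plans also allow an optional regression of restraint selection on group. This part of the objection stands, and it makes the consequence conditional.

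It can also be said that the fallback need not be reached. Bounded scores do not by themselves invalidate the planned model: on simulated 8-item data with 60 per arm, the parametric group-by-time test kept its size at roughly 4% to 6%, including a case moving from 85% to 90% correct. That is fair. Equally, a strict normality test on raw 8-item scores would flag nearly every sample, and the plans do not say how normality will be judged. How likely the trigger is cannot be settled from the protocol.

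The scenarios in which arm effects cancel are contrived. Nothing suggests that reading recommendations would lower scores in some arms just enough to offset gains in others. They show what the test ignores and do not estimate an error rate for this trial. The near-100% figure is likewise a correct rejection of no change over time; it misleads only if read as a version effect.

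Finally, the exact fallback is often left to a statistical analysis plan. That would excuse silence. Here the protocol names a test, presents it as appropriate, and repeats it in both plans.

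**Conclusion.** The point holds in a limited form. In both studies, the only nonparametric test named as a replacement for the Time x Group analysis tests neither group nor group-by-time. This follows from the algebra and does not depend on the simulations. If transformation is not used and the named test is, the question of which version or combination works best would go untested. A significant result would then show only an overall pre-post change (about 100% rejection when all arms gain equally, under the stated assumptions).

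The flaw sits in a contingency clause with other ways out, so it is worth correcting but does not undermine the main analysis.

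**What to change.** In the Data Analysis Plans of Study 1 and Study 2, replace the Friedman test with a nonparametric comparison of the randomised groups. Suitable choices are rank ANCOVA of posttest adjusted for pretest, or Kruskal-Wallis on the pre-post change, each with multiplicity-adjusted pairwise follow-ups. Alternatively, keep the planned Time x Group model and take permutation p-values for the group-by-time effect. One of these should be named in advance.

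The cost is one sentence in each plan. It needs no new data, no change in sample size and only standard methods.
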